9.4 STATISTICAL ANALYSES

9.4.1 GENERAL APPROACH

Randomization. Randomization will take place centrally via a web-based central randomization system (described above) developed by the National Data Management Center (NDMC).

Multiplicity and Control of Type I Error. Inflation of the type-I error through multiple hypothesis testing is controlled using a sequentially rejective multiple test procedures approach to address repeated testing of pairwise comparison and hypothesis tests of multiple primary, secondary, and exploratory endpoints. This method, which generalizes the approach for closed testing procedures including Bonferroni-Holm, fixed sequence, fallback, and gatekeeping procedures, defines the sequence in which hypotheses and families of hypotheses are tested and sequentially allocates the local type I error rate to guarantee strong control of the familywise error rate (i.e. the probability of incorrectly rejecting at least one true null hypothesis given any configuration of true or false null hypotheses). This approach also provides corresponding methods for correctly specifying the adjusted p-values and confidence intervals with a minimum of $1-\alpha$ coverage. The primary and secondary aims will each test a sequence of null hypotheses comparing 1) whether a difference exists among the three treatment groups, 2) whether Moderate and High Dose I-ACQUIRE each differ from U&CT, and 3) whether Moderate Dose I-ACQUIRE is different from High Dose I-ACQUIRE at a local familywise two-sided type I error rate of 5%. A given hypothesis may only be tested if the previous hypothesis has been rejected.

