4 STUDY DESIGN

4.1 OVERALL DESIGN

The proposed study is a Phase III trial powered to determine efficacy of two different doses of I-ACQUIRE for children 8 to 24 months old with PAIS and hemiparesis. The design is a prospective RCT in which 240 children will be randomly assigned to one of 3 treatment groups (N=80 per group): 1) Moderate Dose I-ACQUIRE (3 hrs/day, 5 day/wk X 4 wks), 2) High Dose I-ACQUIRE (6hrs/day, 5 days/wk X 4 wks), or 3) Usual and Customary Treatment (U&CT). I-ACQUIRE will be delivered by protocol-trained therapists and monitored weekly for dosage and treatment fidelity; U&CT will be provided by community therapists with dosage and approaches documented weekly. All primary and secondary efficacy outcomes rely on blinded assessments at baseline, end of treatment, and 6 mos post-treatment. Exploratory outcomes and supplemental clinical measures may provide valuable additional data about development and health in this sample of children with PAIS.

There will be a second phase of the I-ACQUIRE Study for the children who had been randomly assigned to Group 3 (Usual and Customary Treatment). Their parent(s) may choose to enroll (via a new IRB-approved consent process) to have their child randomly assigned to receive either the Moderate or High Dose I-ACQUIRE treatment. This will occur after the 6-mos Post-Treatment Assessment from the primary phase. Outcome data from this second or crossover phase of the study will not be used in the primary data analysis for this trial but will be available for exploratory and post hoc data analyses.

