9 STATISTICAL CONSIDERATIONS

9.1 STATISTICAL HYPOTHESES

1. Primary Aim: Determine the efficacy of I-ACQUIRE at 2 dosage levels compared to U&CT to increase upper extremity skills on the hemiparetic side. The primary efficacy outcome is a gain and retention of ≥ 7 new skills on the Emerging Behaviors Scale (EBS) at the end of the 4-wk treatment and 6 mos. later.

Hypothesis 1A: The 3 groups will differ significantly in the proportion of infants meeting primary efficacy criteria.
Hypothesis 1B: Both the Moderate Dose and High Dose I-ACQUIRE groups will have significantly higher proportions of infants meeting the primary efficacy criteria compared to U&CT.

Hypothesis 1C: The High Dose compared to Moderate Dose I-ACQUIRE group will have a significantly higher proportion of infants meeting the primary efficacy criteria.

Additional sensitivity analyses using repeated EBS scores (from 0 – 30) will explore specific aspects of treatment outcome and maintenance (e.g., differential magnitude of EBS changes across treatment groups) in relationship to predictor variables (e.g., stroke CNS damage coded from MRI scans, family engagement levels).

2. Secondary Aim: Determine the efficacy of I-ACQUIRE at 2 dosage levels compared to U&CT to improve use of the hemiparetic upper extremity in bimanual activities. The secondary efficacy outcome is the Mini Assisting Hand Assessment score at the end of 4-wk treatment and 6 mos. later.

Hypothesis 2A: The 3 groups will differ significantly in mean Mini AHAs at end of treatment and 6 mos later.

Hypothesis 2B: Both the Moderate Dose and High Dose I-ACQUIRE groups will have significantly higher mean Mini AHAs compared to U&CT at the end of treatment and 6 mos later.

Hypothesis 2C: High Dose compared to Moderate Dose I-ACQUIRE will have significantly higher Mini AHAs at end of treatment and 6 mos later.

3. Exploratory Aim: Explore the association between I-ACQUIRE treatment at Moderate and High Doses and gross motor development and cognition (i.e., cross-domain effects of treatment).

3A. Evidence-informed prediction for motor development: Both Moderate and High Doses of I-ACQUIRE will have higher mean gains in Gross Motor skills compared to U&CT at end of treatment and 6 mos later.

3B. Theory-informed prediction about cognition: High Dose I-ACQUIRE will be associated with larger mean gains in Cognition (Bayley-4) than Moderate Dose I-ACQUIRE and U&CT at 6 mos post-treatment.

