9.2 SAMPLE SIZE DETERMINATION

The proposed minimal clinically meaningful threshold on the primary efficacy is a gain of 7 points after receiving High Dose I-ACQUIRE. We estimate 70% of children in the High Dose group will meet the primary efficacy outcome of ≥ 7 new EBS skills threshold at both post-treatment assessments. We further project that only 40% of the children in the Moderate Dose group will show primary efficacy, because we anticipate higher levels of decline over the 6-mth post-treatment period compared to those in the High Dose group. That is, we predict the new EBS skills at end of treatment will be less permanently established for subjects in the Moderate compared to High Dose group. Thus, to detect a minimal clinically meaningful difference in the primary efficacy outcome between the High and Moderate Dose groups with a two-sided type I error rate of 5% and 90% power, we would need a final randomized sample of $N=57$ subjects in each of the 3 groups. The sample size further inflates the required sample size to ensure adequate power after accounting for up to 15% of subjects lost to follow-up or missing outcome data using an inflation rate of 1.39¹⁰⁹.

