We have limited data about precise EBS changes in children with PAIS receiving U&CT; thus, we relied on U&CT changes from 2 – 6 yr olds and from our clinical database. We estimate up to 15% of U&CT children may meet criteria for the primary outcome, because more families and therapists know about evidence supporting high therapy dosages and CIMT, and thus more U&CT children may be obtaining more effective therapy than in the past (when systematic reviews were conducted and published about many forms of U&CT). We have >80% power to detect a clinically significant treatment difference between either the Moderate Dose or High Dose I-ACQUIRE group and U&CT for any active treatment effect with $\geq 40\%$ of children with favorable outcomes. Finally, although the trial is specifically powered to detect differences in the primary outcome, given the total sample size of $N=240$ and a 5% type I error rate, the secondary and exploratory endpoints have $\geq 80\%$ power to detect pairwise differences in mean change as small as 5 units when the standard deviation is 10. Further note that power and sample size calculations use the conservative assumption of single-time point models and unadjusted analyses; in general, covariate-adjusted repeated measures models will have increased power to detect differences.

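### High vs Moderate is sized at 90% power as a stand-alone test but may be tested only after both doses beat U&CT; the sequence delivers 77% on the same base, and the extra gate is not needed for error control

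*Protocol*

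**What the plan says.** Section 9.2 of the protocol gives the planning rates: "We estimate 70% of children in the High Dose group will meet the primary efficacy outcome", "only 40% of the children in the Moderate Dose group will show primary efficacy", and "We estimate up to 15% of U&CT children may meet criteria for the primary outcome". The sample size is set to detect the difference "between the High and Moderate Dose groups with a two-sided type I error rate of 5% and 90% power". The result is "we would need a final randomized sample of $N=57$ subjects in each of the 3 groups", multiplied by 1.39 to allow for up to 15% missing outcomes. Section 4.1 has the final figure: "240 children will be randomly assigned to one of 3 treatment groups (N=80 per group"). For either dose against U&CT, 9.2 claims only more than 80% power, for an active rate of at least 40%.

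Section 9.4.1 fixes the testing order within each aim: first the three-group test, then whether Moderate and High each differ from U&CT, then Moderate against High, at a local familywise 5%. It adds: "A given hypothesis may only be tested if the previous hypothesis has been rejected". Hypothesis 1B in section 9.1 describes the second step as a joint claim: "Both the Moderate Dose and High Dose I-ACQUIRE groups will have significantly higher proportions of infants meeting the primary efficacy criteria" compared with U&CT.

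Section 9.4.2 scores missing outcomes as unfavorable on the premise that fewer than 5% are missing, and switches to multiple imputation above that.

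**The concern.** The comparison that determines the sample size is the last one in the sequence, and 9.2 computes its power as if nothing came before it. Its real power is the probability that all the earlier tests reject as well.

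The weak link is Moderate versus U&CT. It has less than 90% power at the 57-per-group base, and it shares the Moderate arm with High versus Moderate. When Moderate happens to do poorly, the High–Moderate gap widens but Moderate versus U&CT tends to fail. The gate therefore closes in the samples where the dose test would most likely succeed. Section 9.2 itself expects the Moderate group to lose more of its gains over six months, so a weak Moderate arm is a plausible outcome for this trial. At stake is whether the trial can make a formal claim on the dose question for which it was sized.

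**Working it through.** **Inputs (section 9.2 unless noted).** Success rates: High 0.70, Moderate 0.40, U&CT 0.15 (given as an upper estimate). Two-sided 5%. Base n = 57 per group, 80 after inflation (4.1). Reading used: both second-step tests must reject before High versus Moderate is tested.

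**1. Reproduce the protocol's figure.** With p̄ = 0.55, the common formula gives n = (1.960 + 1.282)² × 2 × 0.55 × 0.45 / 0.30² = 57.8 per group. The version with separate null and alternative variances gives 56. The stated 57 lies between them. Inflation: 1/0.85² = 1.384, and 57 × 1.39 = 79.2, rounded up to 80. The 90% is correct for the stand-alone comparison.

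**2. Power of each link at n = 57** (exact binomial, pooled z tests): High vs Moderate 90.4%; Moderate vs U&CT 86.7%; High vs U&CT and the three-group test both about 100%.

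**3. Power of the sequence.** Summing over the possible numbers m of Moderate successes:

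P(sequence) = Σ P(M = m) × P(High beats m) × P(m beats U&CT) = 77.1%.

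High vs U&CT and the three-group test are treated as satisfied, since each has power of about 100%. If the two links were independent, the product would be 0.904 × 0.867 = 78.3%; the shared Moderate arm lowers it further. Simulation of the full sequence, three-group test included, also gives 77.1%, and Wald tests from a logistic model give 76.3%.

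**4. The same calculation under other conditions.**

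| Condition (rates 15/40/70% unless stated) | High vs Moderate, no second-step gate | Sequence as written |
|---|---|---|
| n = 57, the base for the 90% | 90.4% | 77.1% |
| 80 randomized, 15% missing scored unfavorable (rates × 0.85) | 90.2% | 80.7% |
| 68 evaluable (80 × 0.85; approximates multiple imputation) | 94.5% | 86.3% |
| 80 randomized, 5% missing scored unfavorable (rates × 0.95) | 95.4% | 89.5% |
| 80 randomized, none missing | 97.1% | 92.6% |
| n = 57, U&CT 10% | 90.4% | 87.7% |
| 68 evaluable, U&CT 10% | 94.5% | 93.4% |
| n = 80, none missing, Moderate 30% | over 99% | 63% |
| n = 80, none missing, Moderate 25% | over 99% | 35% |

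The last two rows are sensitivity assumptions, not protocol rates. They assume complete data, so compare them with the 92.6% row rather than the 80.7% row.

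**5. Is the gate needed for error control?** With three groups, if any two pairwise nulls are true, all three groups are equal, so every intersection of pairwise nulls is the global null. By the closed testing principle, once the three-group test rejects at 5%, each pair may be tested at 5% with strong familywise control. Simulated familywise error of that rule, at 57 and 80 per group over seven null configurations, was 4.7% to 5.2%, which is nominal apart from binomial discreteness.

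**6. Cost of keeping the gate at 90% sequential power.** About 74 effective subjects per group are needed: 74 × 1.39 = 102.9, so 103 per group, or 309 in total instead of 240.

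**The case against.** Four points against deserve weight.

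- **A reader might infer that the trial as run has only 77% to 81% power for the dose comparison.** The documents do not support that as a general statement. The 77% belongs to the 57-per-group base, whereas 80 per group are randomized. The 81% scores 15% missing as failures, a case in which 9.4.2 would use multiple imputation instead. Under the protocol's own missing-data rules the sequence has about 86% to 93%, and more if U&CT is below its 15% ceiling. This stands. The ungated test gains from the same conditions, however, so the gate still costs roughly 5 to 8 points there.
- **The second step holds two hypotheses.** If rejecting either one opened the third step, power would remain about 90% at n = 57. Section 9.4.1 describes a general sequentially rejective framework, and the opening rule might be detailed elsewhere. The wording of 9.4.1 and Hypothesis 1B favors requiring both, but this is a reading and should be named as one.
- **The order may be deliberate.** Requiring each dose to beat usual care before ranking the doses is a legitimate hierarchy. In that case 9.2 should report the power that the hierarchy delivers.
- **The 63% and 35% figures lie outside the planning claim**, which covers active rates of at least 40%. They show how the gate behaves with a weaker Moderate arm; they are not planned power.

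A reader might also infer that if only High works the trial shows nothing. That goes too far: High versus U&CT is still tested in the second step, and the dose difference can still be estimated. What is lost is the formal High versus Moderate test.

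**Conclusion.** The point holds as a mismatch between sizing and testing order. The 90% is arithmetically right for a stand-alone test, but 9.4.1 does not permit a stand-alone test. On the same 57-per-group base the sequence gives 77%. At 80 per group it gives about 81% to 93%, depending on missing data, against 90% to 97% without the second-step gate. At the planning rates the gate costs roughly 5 to 13 points, less if U&CT is below 15% and much more if Moderate falls below 40%. It gives no familywise protection beyond the three-group test. These figures rest on the protocol's rates, on unadjusted tests as assumed in 9.2, on 68 evaluable per group as a stand-in for multiple imputation, and on both second-step tests having to reject. The matter should be settled before unblinding, but it does not threaten the validity of the trial.

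**What to change.** Preferred change, in 9.4.1: after the three-group test rejects at 5%, test each of the three pairwise comparisons at two-sided 5% as a closed test. Apply this within Aim 1 and within each Aim 2 family (six months, then end of treatment). State that the next family opens only if all three pairwise nulls are rejected. That keeps the present opening condition, because the existing sequence also reaches its end only when every test has rejected.

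The adjusted p-value for a pair is then the larger of the three-group p-value and the pairwise p-value. The method for the adjusted confidence intervals promised in 9.4.1 should be restated to match.

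If the sequence is kept: replace the 90% in 9.2 with the sequential power for High versus Moderate (77% at n = 57; about 81% to 93% at 80 per group, depending on missing data), and say explicitly that both second-step tests must reject to open the third.

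Either route is a wording change to the protocol and analysis plan, with no additional subjects. The closed test gives up no familywise error control.

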9.4.2 ANALYSIS OF THE PRIMARY EFFICACY ENDPOINT(S)

The primary analysis (Aim 1) will use a modified intent-to-treat (mITT) study sample defined as those subjects who attend the baseline visit and continue to meet eligibility. This approach will permit exclusion of subjects who are randomized, but then drop out prior to any baseline data being collected, due to changes in eligibility or family circumstances that preclude any study participation. The sample size for analysis will be 240 subjects who meet the mITT definition.

Missing outcomes will be imputed as unfavorable, which is a conservative but reasonable approach given minimal (<5%) missing data. If the amount of missingness is unexpectedly high, e.g. >5%, then missing primary outcome data will be imputed via standard multiple imputation methods (i.e., via logistic regression model predicting outcome based on pertinent baseline and treatment data). The primary analysis will test the sequence of null hypotheses using fitted estimates from a logistic regression model, where the dependent variable is the dichotomized indicator of a favorable outcome, ≥ 7 new EBS skills above baseline at the end of 4-wk treatment and 6 mos post-treatment. An interim analysis for futility is planned after $N=120$ ($N=$ approximately 40/group) subjects complete the 6-month post-treatment visit using a non-binding O'Brien and Fleming type stopping boundary. Sensitivity analyses of the primary analysis will also consider the impact of distribution-based methods, using a generalized linear mixed-effects repeated measures model where change in EBS is modeled as continuous and the model is adjusted for baseline EBS score, treatment group, study visit (4 weeks or 6 months), and an interaction for treatment group and visit. Subgroup analyses will evaluate the impact of race/ethnicity, gender, neuroimaging biomarkers of injury, therapy fidelity, and parental involvement. The impact of U&CT dose variability will also be assessed in a model where the categorical indicator for treatment group will be replaced by a continuous covariate measuring total hours of therapy received and a categorical indicator for type of therapy.

Data analysis and management. The NDMC will be performing all the primary data analysis and management. All activities will be conducted in coordination with the participating clinical sites, Executive Committee, and the IOC. Case report forms will be developed and distributed to clinical sites prior to study initiation.

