6.3 MEASURES TO MINIMIZE BIAS: RANDOMIZATION AND BLINDING

Subjects will be randomized in a 1:1:1 fashion to U&CT, Moderate Dose I-ACQUIRE, or High Dose I-ACQUIRE using a restricted randomization algorithm which controls for within site treatment imbalances. If no imbalances exceed the tolerated threshold, the patient is randomized according to the specified allocation ratio (1:1:1) using a block urn design. If an unacceptable level of imbalance exists, the algorithm will determine whether the current allocation ratio improves or exacerbates the current imbalance and adjust the ratio accordingly. The detailed randomization scheme and source codes will be provided in the Randomization Plan document. Note: for general understanding, the randomization process will be described in the consent document for parents as having an equally fair chance of being assigned to one of the 3 treatment groups.

Upon confirmation of eligibility and obtaining parental permission to participate, study coordinators will log into the WebDCU™ study database and receive the computer-generated randomization assignment. Local Site Coordinators will notify families promptly to schedule baseline assessments and designate the treatment month.

It is not possible to blind the family or the treatment team; however, no treating therapist will conduct assessments for primary and secondary outcomes, and none of the blinded assessors will work in the same setting as treatment staff. In addition, the primary and secondary outcomes will be coded by staff at the Central Assessment Core at The Ohio State University, remote from the clinical site and treatment implementation core. Assessment Core research staff will be blinded to treatment and the videos will be randomly sorted so that central coders cannot know whether a video is the baseline or one of the follow-up assessments. Parents also are reminded before each assessment session not to discuss their child's treatment with the assessor.

For assessments completed by the local blinded assessor, a second blinded scoring will be calculated by the central blinded assessment team if the local assessor has indicated that he or she possibly has become unblinded. Only blinded scores will be used in the primary analysis, but sensitivity analyses will compare the local and central scores to assess for any potential differences due to the unblinding.

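### Section 9.4.2 names no covariates for the primary logistic model; baseline EBS and age should be specified in it, for a modest gain in power

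*Protocol*

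**What the plan says.** **Primary model.** Section 9.4.2 states: "The primary analysis will test the sequence of null hypotheses using fitted estimates from a logistic regression model". It defines the dependent variable (a gain of at least 7 EBS skills at both follow-up assessments) and lists no covariates. It does not call the model unadjusted.

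**Sensitivity model.** The same section lists the terms of the model for continuous EBS change: baseline EBS, treatment, visit and their treatment-by-visit interaction.

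**Age.** Age is not among the subgroup factors in 9.4.2. The COVID-19 addendum (11.1) leaves the effect of treating children older than the original 24-month limit to post hoc work.

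**Power.** Section 9.2 notes that "power and sample size calculations use the conservative assumption of single-time point models and unadjusted analyses", and adds that covariate-adjusted repeated measures models generally have more power.

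**Randomization.** Section 6.3 assigns children "using a restricted randomization algorithm which controls for within site treatment imbalances". No other balancing factor is named. The baseline assessment is scheduled after assignment, and families and treating staff are not blinded.

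**Analysis sample.** Sections 9.3 and 9.4.2 remove from the mITT sample children who leave, or cease to be eligible, before baseline.

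**The concern.** The endpoint is a threshold on change, so two baseline quantities are likely to bear on it. The first is the starting score: sections 5.2 and 8.1 both say that a high baseline rules success out. The second is age: section 4.2 describes rapid upper-extremity development over the first three years and says plasticity may vary with age. Section 9.4.2 itself treats baseline data as informative, because its multiple-imputation model would predict the outcome from them.

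The order of events adds a reason beyond power. Families know the arm before baseline, and those who leave in between are dropped. Differences in baseline EBS or age between the analysed arms could then reflect selection after assignment as well as chance. Adjustment corrects for the measured part of such differences.

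At stake are some power on each test in the sequence, where a later test is reached only if the earlier ones reject, and a clear prior statement of which model gives the primary result.

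**Working it through.** **1. Inputs from section 9.2.** The design is set "with a two-sided type I error rate of 5% and 90% power". The success rates are "We estimate 70% of children in the High Dose group", "only 40% of the children in the Moderate Dose group", and for the control arm "We estimate up to 15% of U&CT children may meet criteria for the primary outcome". The size is N=57 "subjects in each of the 3 groups", inflated by 1.39 for up to 15% loss. Section 4.1 gives 80 per arm and 240 in total.

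**2. The plan's own figure.** For 70% vs 40%, with pooled variance and no continuity correction:

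n = [1.960·√(2·0.55·0.45) + 1.282·√(0.70·0.30 + 0.40·0.60)]² / 0.30² = (1.379 + 0.860)² / 0.09 ≈ 56

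The stated 57 is reproduced to within one child. Then 57 × 1.39 = 79.2, so 80 per arm and 240 in total.

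**3. Unadjusted power at the stated rates**

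| Per arm | Moderate vs U&CT (40 vs 15%) | High vs Moderate (70 vs 40%) |
|---|---|---|
| 57 | 85.8% | 90.7% |
| 68 (= 0.85 × 80) | 91.3% | 94.9% |
| 80 | 95.0% | 97.4% |

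**4. Effect of adjustment, by simulation.** The protocol gives no prognostic strength for baseline EBS or age, so this is assumed over a range. The runs used three arms, marginal rates held at 15/40/70%, and Wald tests at two-sided 5% (2,000 runs per scenario). The combined covariate effect has SD s on the logit scale. Its share of latent variance is s²/(s² + 3.29), which is 7% for s = 0.5, 23% for s = 1.0 and 41% for s = 1.5. The last case also has a site SD of 0.3.

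| Per arm | s | Moderate vs U&CT, unadjusted → adjusted | High vs Moderate, unadjusted → adjusted |
|---|---|---|---|
| 80 | 0.5 | 95.2 → 95.8% | 97.1 → 98.0% |
| 80 | 1.0 | 94.5 → 97.0% | 97.4 → 98.6% |
| 80 | 1.5 | 93.6 → 98.4% | 97.3 → 99.7% |
| 57 | 0.5 | 85.4 → 86.4% | 90.7 → 91.8% |
| 57 | 1.0 | 85.0 → 89.4% | 90.3 → 95.0% |
| 57 | 1.5 | 85.0 → 93.9% | 89.9 → 96.5% |

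A separate simulation set directly at 10-30% of latent variance gave gains of about 1-3 points at 80 per arm, 1-4 at 68 and 1-8 at 57.

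**5. Type I error at 80 per arm (all arms 40%).** The unadjusted model rejected in 4.4-4.8% of runs and the model with the two covariates in 4.5-4.8%. Adding 11 fixed site indicators gave 5.2-6.2%.

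**6. Site.** Section 5.5 plans 12 or more sites. 240 / 3 / 12 = 6.7 children per arm per site at most, and 0.15 × 6.7 ≈ 1 expected U&CT success per site. Site indicators added 2 points of power or less beyond the two covariates, and up to about 2 of these appeared even when no site effect was simulated.

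**The case against.** **Silence is not a choice.** A reader might infer that the protocol fixes an unadjusted primary analysis and so gives up power. It does not. Section 9.4.2 lists no right-hand-side terms for the primary model, and the remark in 9.2 describes the power calculation, which it calls conservative. Covariates are commonly left to the SAP, which may already list them. This stands, and limits the point to a specification the protocol should carry.

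**Prognostic strength is not shown.** Section 8.1 says the threshold works over the whole EBS range, and section 2.2 reports gains of this size from baselines of 0 to 23. Those statements concern how well the threshold classifies and do not show that success is independent of baseline. Still, headroom is documented only near the ceiling, so the assumed 10-30% remains an assumption.

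**Power is not short.** Counting the whole 15% loss as failures (rates of 12.75/34/59.5%) lowers unadjusted power at 80 per arm to about 90% and 91%. That is not the plan's rule: 9.4.2 imputes failure only when missingness is minimal and moves to multiple imputation above 5%.

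**Balance and validity.** It is tempting to say that neither covariate could have been balanced by randomization. This is true of baseline EBS only; age is known when eligibility is confirmed. Nor is the unadjusted test invalid: chance imbalance is already covered by its error rate, and omitting site generally makes the test slightly conservative.

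**Conclusion.** The point holds as an improvement to the specification of the primary model. It is not an error in the sample size, which reproduces. Naming baseline EBS and age uses data already collected, keeps type I error near 5% in simulation, and handles measured differences that arise between assignment and baseline. It would not remove selection on unmeasured factors.

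The gain is about 1-3 points at 80 per arm with complete data, and about 1-4 points at 68 per arm if 15% are lost. Both figures assume that the covariates explain 10-30% of latent outcome variance; with weaker covariates the gain is close to nil. The documents do not support a demand that site enter the primary model: the counts per site are small, and fixed indicators pushed the simulated error rate slightly above 5%.

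**What to change.** In 9.4.2, before the N=120 futility look:

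- State that the primary logistic model contains treatment, baseline EBS (continuous) and age at treatment start (continuous).
- Report covariate-standardized risk differences beside the odds ratios, and say that the odds ratios are conditional on the covariates.
- Keep the unadjusted model as a sensitivity analysis, and examine site in another.

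If the SAP already specifies this, align the protocol with it. The cost is a few sentences and no new data. The one small downside is that the odds ratio becomes conditional, which the standardized risk differences offset.
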